9.4. Subject Status and Classification

Subjects are enrolled once they complete the informed consent process. However, some subjects may not meet all inclusion/exclusion criteria and subsequently are not counted toward the enrollment ceiling. The following definitions are intended to classify subjects based on their study eligibility:

- Consent Ineligible: A subject who has signed the ICF but is found to not meet eligibility criteria. The subjects will be exited and will not undergo any study related procedures once their ineligibility has been determined. These subjects do not count toward enrollment.
- Exited Prior to Procedure: A subject who signs the informed consent, meets eligibility criteria, but then does not have the study procedure initiated (first incision). The original ICF and screening documentation for these patients should be maintained in the site's files. There are no follow-up requirements and any data collected prior to procedure is not included in statistical analyses.
- Intent to Treat: A subject who signs the informed consent, and for whom the index procedure is initiated (first incision). The original ICF and screening documentation for intent to treat patients should be maintained in the site's files. These patients are followed in accordance with the study follow-up schedule and count toward enrollment.

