11.2. General Statistical Methods

The Intent-to-Treat (ITT) subject population includes all subjects who provide written informed consent to be enrolled into the study, and have a surgery initiated (defined as the first incision).

The As Treated (AT) Population includes all subjects for whom implantation of the device is successful.

The Per Protocol (PP) population includes all subjects in the AT Population who meet all eligibility criteria and have no major protocol deviations.

The endpoint analyses will be performed for the ITT population. The AT and PP populations will be evaluated as sensitivity analyses for the primary endpoint, and the safety outcomes will also be assessed using AT population.

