26.2. Definitions

Terms are defined in Table 26.2-1-1.

Table 26.2-1: Definitions

	Table 20.2-1. Definitions
Term	Definition
Adverse Device Effect	See Table 18.2-1, Safety Definitions
Adverse Event	See Table 18.2-1, Safety Definitions
As Treated	All subjects for whom implantation of the device is attempted.
Consent Ineligible	A subject who has signed the ICF but is found to not meet eligibility criteria. These subjects can still receive the AMS 800 per standard of care treatment, but do not count toward enrollment. The subjects will be exited and will not undergo any study related procedures once their ineligibility has been determined. These subjects do not count toward enrollment.
Data Controller	In GDPR: The entity which determines the purposes (why the entity needs to process data) and means (database managed through a software, hard copy files, centralized database) of personal information processing.
Data Processor	In GDPR: The person or entity processing the data on behalf and according to the instructions of the data controller. An entity which uses an external data processor must ensure that, in the contract, its data processor offers adequate guarantees to ensure the security and confidentiality of the data communicated.
Data Subject	In GDPR: Any living individual to whom the personal data relates. Examples of data subjects in this study are physicians and subjects.
Deviation (Clinical Protocol)	A departure from the requirements established in the clinical trial protocol (e.g., inclusion/exclusion criteria; visit windows, required procedures, and any specified consenting process requirements).
Exited Prior to Procedure	A subject who signs the informed consent, meets eligibility criteria but then does not undergo having the index study procedure initiated (first incision) or receive the study device. The original ICF and screening documentation for these patients should be maintained in the site's files. There are no follow-up requirements and these subjects do not count toward enrollment. Any data collected prior to procedure is not included in statistical analyses. These subjects do not count toward enrollment.
General Data Protection Regulation (GDPR)	The General Data Protection Regulation (GDPR) is a European law that will govern how companies (whether EU-based or not) use personal data.
Hospitalization	See Table 18.2-1 Safety Definitions

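### Consent Ineligible carries no time limit, so a man found ineligible after first incision falls under both the exit rule and the ITT follow-up rule, and the glossary ITT entry adds to the conflict

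*Combined protocol and SAP*

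**What the plan says.** Section 9.4 sorts consented subjects into three classes.

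- **Consent Ineligible:** "A subject who has signed the ICF but is found to not meet eligibility criteria". The consequence is "The subjects will be exited and will not undergo any study related procedures once their ineligibility has been determined", and "These subjects do not count toward enrollment".
- **Exited Prior to Procedure:** a man who "meets eligibility criteria, but then does not have the study procedure initiated (first incision").
- **Intent to Treat:** "A subject who signs the informed consent, and for whom the index procedure is initiated (first incision"). For this class, "These patients are followed in accordance with the study follow-up schedule and count toward enrollment".

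Sections 9.1 and 11.2 also define ITT by consent and first incision, with no eligibility condition. The PP population in Section 11.2 "includes all subjects in the AT Population who meet all eligibility criteria and have no major protocol deviations".

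The glossary (Table 26.2-1) repeats the Consent Ineligible definition, again without a time limit, and adds: "These subjects can still receive the AMS 800 per standard of care treatment, but do not count toward enrollment". Its ITT entry differs from the body text: it requires that the subject be eligible, and it describes the procedure as started but left unfinished.

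**The concern.** The second class is bounded by first incision; the first is not. A man whose eligibility failure surfaces after implantation, for example when monitoring turns up a culture result or an HbA1c value, therefore meets the wording of both the first and the third class. One tells the site to end his participation and not count him. The other tells it to keep him on schedule and count him. No sentence gives either precedence.

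If the site ends his participation, his study data probably stop. Section 18.1 ties event reporting to the period of participation. Section 9.2 says further data may not be collected once a subject has been withdrawn, and its provision for asking to follow a man outside the study covers only withdrawals linked to device safety or performance. The Month 12 pad weight would then be missing, and later serious events and revisions would go unrecorded.

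**Working it through.** No figure in the plan bears directly on this point, so the check is mainly a comparison of texts.

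**1. The definitions side by side**

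| Text | Eligibility | First incision | What follows |
|---|---|---|---|
| 9.4 Consent Ineligible | must fail | not mentioned | exit, not counted |
| 9.4 Exited Prior to Procedure | must pass | must not have happened | no follow-up, data not analysed |
| 9.4 ITT | not mentioned | required | followed, counted |
| 9.1 and 11.2 ITT | not mentioned | required | in the ITT population |
| Table 26.2-1 ITT | must pass | required, procedure unfinished | safety follow-up, counted |
| 11.2 PP | must pass | required (implanted) | sensitivity analysis |

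**2. A test case.** Take a consented man with a completed implant who is found ineligible some weeks later.

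- 9.4 Consent Ineligible: he fits.
- 9.4 Exited Prior to Procedure: he does not fit, on either condition.
- 9.4, 9.1 and 11.2 ITT: he fits.
- Table 26.2-1 ITT: he fails twice, because he is ineligible and because his procedure was finished. Read literally, this entry would also leave out every eligible man with a completed implant, so it cannot be what was intended.

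**3. Does the plan foresee such men?** Yes. The PP rule in 11.2 filters implanted men on eligibility, which removes someone only if an ineligible man was implanted. Table 26.2-1 lists the entry criteria among the requirements whose breach is a deviation. Table 10.1-1 places the criteria review at screening and baseline, up to 90 days before surgery. The check before implantation in Section 7.2 is that the man still wants the operation; a repeat of the eligibility review is not mentioned.

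**4. What an exit does to the estimates.**

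- *Primary endpoint.* He stays in ITT by definition but has no Month 12 value. Section 11.3 uses available cases unless stated otherwise, and 11.1.1.3 covers missing data by a tipping-point analysis. He becomes one more missing outcome.
- *Serious adverse events and revision.* Sections 11.1.2.1.1 and 11.1.2.2.1 specify Kaplan-Meier, S(t) = Π(1 − d_j/n_j) over event times up to t. Up to exit he counts in n_j, and any event of his counts in d_j. After exit he is censored. The estimate is biased only if his later risk differs from that of the men still followed. That is plausible, since some criteria (immunosuppression, uncontrolled diabetes, earlier prosthesis infection, bleeding disorder, urine culture) seem to concern surgical or infection risk and Section 10.11 names infection and erosion among reasons for revision. The documents do not establish it.

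**5. Sample size.** Inputs from 11.1.1.2 and 11.1.1.3: null 65%, assumed 80%, one-sided 0.025, exact binomial. At n = 96, success needs at least 72 responders; exact type I error is 0.0236 and power 0.909, which reproduces the stated 90%. Attrition: 96 / (1 − 0.20) = 120, also reproduced. The allowance is 120 − 96 = 24 men without an outcome. Exits of this kind would draw on that allowance; they do not alter the calculation.

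**The case against.** The strongest reply is that context makes Consent Ineligible a screening status. Section 7.1 explains over-enrolment by men who fail screening on baseline data after consent. Sections 7.2 and 10.2 put eligibility before treatment, and Table 10.1-1 schedules the review only before surgery. The glossary line "These subjects can still receive the AMS 800 per standard of care treatment, but do not count toward enrollment" makes sense only for a man not yet implanted. This probably is the intent, and it stands. It does not remove the problem, because neither definition says so, while the neighbouring class does state its limit.

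The reply also disposes of three stronger readings that a reader might infer.

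- *That the man drops out of the ITT denominator.* Sections 9.1 and 11.2 keep him in. The remark in 9.4 about not counting relates to enrolment and its ceiling, not to the analysis set. Section 9.2 allows data gathered before withdrawal to be used, unless local rules differ.
- *That the reported revision rate falls by a computable amount.* Deleting such men from numerator and denominator is not the planned analysis; Kaplan-Meier censors them at exit. Any figure would rest on an assumed frequency and an assumed event rate, neither of which the documents give.
- *That the plan orders safety follow-up of an implanted man to stop, or leaves him without care.* No text says this of implanted men. Section 15.2 requires adequate medical care for adverse events during and after participation. What may end is study data collection, as a consequence of a site's reading.

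Deviations already have to be reported under Section 14, and 11.2 already removes ineligible men from PP. So part of the remedy exists; the missing part is the rule of precedence and a consistent glossary.

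**Conclusion.** The concern holds as a conflict between stated rules. After first incision an ineligible man meets two classes in Section 9.4 with opposite instructions, and the glossary ITT entry contradicts Sections 9.1, 9.4 and 11.2. The analysis set itself is settled by 9.1 and 11.2. What remains is an operational risk: a site relying on the exit rule or the glossary may stop his data collection, giving a missing primary outcome and possibly informative censoring of serious adverse events and revisions.

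The number of men affected is unknown and probably small. The size and direction of any bias cannot be derived from the documents; a downward bias in the safety rates would require that these men carry higher later risk, which is plausible but unproven. The sample size and primary test are unaffected. The passages should be reconciled, since the correction costs almost nothing.

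**What to change.** Three wording changes.

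1. In Section 9.4 and Table 26.2-1, limit Consent Ineligible to subjects whose ineligibility is found before first incision.
2. In the same places, state that a subject found ineligible after first incision remains ITT on the existing follow-up schedule, is recorded as a protocol deviation, and is excluded only from the PP population.
3. In the ITT entry of Table 26.2-1, remove the eligibility condition and the words describing the procedure as unfinished, so that it agrees with Sections 9.1, 9.4 and 11.2. Without this third change the glossary would still deny ITT status to the same man.

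The cost is a few sentences in an amendment. No visits are added beyond the ITT schedule already planned, and the sample size, test and analysis populations in Section 11 stay as they are.

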9.5. End-of-Study Definition

The clinical trial is considered completed when participants are no longer being examined or the last participant's last study visit has occurred.

A participant is considered to have completed the study if he has completed the Month 12 visit as shown in the Data Collection Schedule (see Section 10 for details).

The end of the study is defined as completion of the final Clinical Study Report.

10. Study Methods

10.1. Data Collection

The data collection schedule is shown in Table 10.1-1. All study data will be recorded on source documentation and captured within Case Report Forms (CRFs) for the purposes of this study. Study data will be monitored by Boston Scientific or representatives and as applicable on a regular basis as outlined in the study Monitoring Plan.

Table 10.1-1: Data Collection Schedule

Procedure/Assessment	Screening / Enrollment Visit²	Pre-Operative / Baseline Visit (≤90 calendar days before index procedure)	Index Procedure (≤90 calendar days from screening visit)	Device Activation (30-45 calendar days post index procedure)	Follow-up Visits ⁴		
					3 Month Visit ⁵ (±6 Weeks)	6 Month Visit ⁵ (± 3 Months)	12 Month Visit ⁵ (± 3 Months)
Informed consent process, including informed consent signature and date	X						
Inclusion/Exclusion Criteria Review	X	X					
Demographics		X					
Physical assessment, including weight and height		X				X^6	X^6
Medical history ¹	X	X					
3-day eDiary		X				X	X
24-hour Pad Weight Test		X		X		X	X
# Pads per Day		X			X	X	X
IQoL (Urinary Incontinence Quality of Life)		X			X	X	X
IIQ-7 (Incontinence Impact Questionnaire)		X			X	X	X
EQ-5D (Health Status)		X					X
Patient Ease of Use Questionnaire						X	X
Index Procedure			X				
Assessment of Adverse Events and Device Deficiencies ³			X	X	X	X	X
End of Study							X

¹Medical History at baseline includes documented absence of urine culture.

²The Screening/Enrollment Visit and Pre-Operative/Baseline Visit may be combined and occur up to 90 calendar days prior to the study procedure with confirmed absence of infection.

³Reportable events include (procedure related) AEs, SAEs, SADEs, ADEs and device deficiencies. Adverse events that are not related to the device and not related to the procedure will not be collected; however, these assessments should be noted in the subject's medical records.

⁴Every effort should be made to do the follow-up visit within the window; however, if this is not possible, the site should attempt to complete the visit as soon as possible, but before the next visit window opens. Follow-up visits will be considered missed once the visit window for the next follow-up visit opens. For the Month 12 visit, the visit is not considered missed until the last day of the visit window. All follow-up visit windows start from the day of device activation.

₅Visits may be conducted in clinic or remote.

⁶Optional assessment. Height and weight may be patient reported.

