18.1. Reportable Events by investigational site to Boston Scientific

It is the responsibility of the investigator to assess and report the following events to BSC if they occurred from the time of index procedure through the end of the subject's participation in the study:

- Serious Adverse Events
- Serious Adverse Device Effects
- Adverse Device Effects
- Procedure Related Adverse Events
- Device Deficiencies

Events to be reported include both anticipated and expected post procedural events, in addition to any other unanticipated and unexpected events.

When possible, the medical diagnosis should be reported as the Event Term instead of individual symptoms.

If it is unclear whether or not an event fits one of the above categories, or if the event cannot be isolated from the device or procedure, it should be submitted as an adverse event and/or device deficiency.

Reportable events must be recorded in the eCRF. The Investigator or designee is responsible for updating the eCRF with new or updated information in relation to the already reported event as soon as he/she becomes aware.

Underlying diseases and chronic conditions are not reported as AEs unless there is an increase in severity or frequency during the course of the investigation. Death should not be recorded as an AE but should only be reflected as an outcome of one (1) specific SAE (see Table 18.2-1 for Safety definitions).

Refer to Instructions for Use for the known risks associated with the commercial device(s).

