18.2. Definitions and Classification

Safety definitions are provided in Table 18.2-1. Administrative edits were made on the safety definitions from applicable regulations and guidance including (but not limited to) 21 CFR Part 812, ISO 14155 and EU MDR 2017/745/MDCG 2020-10/1 Guidance on Safety Reporting in Clinical Investigations for clarification purposes.

Table 18.2-1: Safety Definitions

Term	Definition	
Adverse Event (AE) Ref: ISO 14155 Ref: MDCG 2020-10/1	Any untoward medical occurrence, unintended disease or injury, or any untoward clinical signs (including an abnormal laboratory finding) in subjects, users or other persons, in the context of a clinical investigation whether or not related to the study medical device and whether anticipate or unanticipated. NOTE 1: This includes events related to the study medical device or comparator. NOTE 2: This definition includes events related to the procedures involved.	
	NOTE 3 : For users or other persons, this definition is restricted to events related to the study medical device.	
Adverse Device Effect (ADE)	Adverse event related to the use of the study medical device	
Ref: ISO 14155 Ref: MDCG 2020-10/1	NOTE 1 : This includes any adverse event resulting from insufficiencies or inadequacies in the instructions for use, the deployment, the implantation, the installation, the operation, or any malfunction of the study medical device.	
	NOTE 2 : This definition includes any event resulting from use error or from intentional misuseof the study medical device.	
	Note 3 : This includes 'comparator' if the comparator is a medical device.	
Serious Adverse Event (SAE)	Adverse event that led to any of the following:	
	a) death,	
Ref: ISO 14155	b) serious deterioration in the health of the subject, user or other persons as defined by either:	
Ref: MDCG 2020-10/1	1) a life-threatening illness or injury, or	
	a permanent impairment of a body structure or a body function, including chronic diseases, or	
	 in-patient hospitalization or prolongation of existing hospitalization, or 	
	4) medical or surgical intervention to prevent life-threatening illness or injury or permanent impairment to a body structure or a body function	
	c) foetal distress, foetal death, or a congenital abnormality or birth defect including physical or mental impairement.	

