18.3. Relationship to Study Deviceand/or Study Procedure

The Investigator must assess the relationship of the reportable event to the study device and/or study procedure. See criteria in Table 18.3-1: .

Table 18.3-1: Criteria for Assessing Relationship of Study Device or Procedure to Adverse Event

Classification	Description
Not Related	Relationship to the device or procedures can be excluded when:
Ref: MDCG 2020-10/1	- the event has no temporal relationship with the use of the study device or the procedures related to the use of the study device;
	- the serious event does not follow a known response pattern to the medical device (if the response pattern is previously known) and is biologically implausible;
	- the discontinuation of medical device application or the reduction of the level of activation/exposure - when clinically feasible – and reintroduction of its use (or increase of the level of activation/exposure), do not impact on the serious event;
	- the event involves a body-site or an organ that cannot be affected by the device or procedure;
	- the serious event can be attributed to another cause (e.g. an underlying
	or concurrent illness/ clinical condition, an effect of another device, drug, treatment or other risk factors);
	- the event does not depend on a false result given by the study device used for diagnosis, when applicable;
	In order to establish the non-relatedness, not all the criteria listed above might be met at the same time, depending on the type of device/procedures and the serious event.
Possibly Related	The relationship with the use of the study device or the relationship with
Ref: MDCG 2020-10/1	procedures is weak but cannot be ruled out completely. Alternative causes are also possible (e.g. an underlying or concurrent illness/ clinical condition or/and an effect of another device, drug or treatment). Cases where relatedness cannot be assessed or no information has been obtained should also be classified as possible.
Probably Related Ref: MDCG 2020-10/1	The relationship with the use of the study device or the relationship with procedures seems relevant and/or the event cannot be reasonably explained by another cause.

Table 18.3-1: Criteria for Assessing Relationship of Study Device or Procedure to Adverse Event

Classification	Description
Causal Relationship Ref: MDCG 2020-10/1	The serious event is associated with the study device or with procedures beyond reasonable doubt when:

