18.4. Investigator Reporting Requirements

The communication requirements for reporting to BSC are as shown in Table 18.4-1.

Table 18.4-1: Reporting Timelines

Event Classification	Communication Method	Communication Timeline post-market studies* (EU MDR 2017/745, MDCG 2020-10/1 MEDDEV 2.12/1: GUIDELINES ON A MEDICAL DEVICE VIGILANCE SYSTEM)
Serious Adverse Event	Complete AE eCRF page with all available new and updated information.	 Within 10 calendar days after becoming aware of the event or as per local/regional regulations. Reporting required through the end of the study.

Page 52 of 62

	I	Page 32 01 02
Event Classification	Communication Method	Communication Timeline post-market studies* (EU MDR 2017/745, MDCG 2020-10/1 MEDDEV 2.12/1: GUIDELINES ON A MEDICAL DEVICE VIGILANCE SYSTEM)
	Provide all relevant source documentation (deidentified/pseudonymized) for reported event.	 When documentation is available (recommend within 60 calendar days) Upon request of sponsor
Serious Adverse Device Effects	Complete AE eCRF page with all available new and updated information.	 Within 3 calendar days of first becoming aware of the event or as per local/regional regulations. Reporting required through the end of the study.
	Provide all relevant source documentation (deidentified/pseudonymized) for reported event.	 When documentation is available (recommend within 30 calendar days) Upon request of sponsor
Device Deficiencies (including but not limited to malfunctions, use errors, and inadequacy in information supplied by the manufacturer,	Complete Device Event CRF with all available new and updated information.	 Within 3 calendar days of first becoming aware of the event. Reporting required through the end of the study.
including labelling) Note: Any Device Deficiency that might have led to a serious adverse event if appropriate action had not been taken intervention had not occurred if circumstances had been less fortunate is considered a reportable event.	Provide all relevant source documentation (deidentified/pseudonymized) for reported event.	Upon request of sponsor.
Procedure-Related Adverse Events and Adverse Device Effects	Complete AE eCRF page, which contains such information as date of AE, treatment of AE resolution,	Adverse Device Effects: In a timely manner but not later than 30 business days after becoming aware of the information.

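### Table 10.1-1 footnote 3 excludes unrelated adverse events without exempting serious ones, which conflicts with section 18 and Secondary Endpoint 1 if read literally

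*Combined protocol and SAP*

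**What the plan says.** Footnote 3 of Table 10.1-1 is attached to the row for adverse events and device deficiencies. Its first sentence lists the reportable events and names SAEs among them; the qualifier about procedure relatedness stands before AEs. Its second sentence gives the exclusion: "Adverse events that are not related to the device and not related to the procedure will not be collected". It adds that such events should be noted in the medical records.

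The safety section is worded differently:

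- Section 18.1 introduces its list with "It is the responsibility of the investigator to assess and report the following events to BSC". The list names SAEs without a qualifier and procedure-related adverse events as a separate item.
- Section 18.1 also says: "Death should not be recorded as an AE but should only be reflected as an outcome of one (1) specific SAE".
- Table 18.2-1 defines an SAE as an "Adverse event that led to any of the following", followed by the seriousness criteria. Its definition of an adverse event applies whether or not the event is related to the device.
- Section 18.3 states: "The Investigator must assess the relationship of the reportable event to the study device and/or study procedure". One class in Table 18.3-1 is for unrelated events: "Relationship to the device or procedures can be excluded when".
- Table 18.4-1 gives SAEs their own row and deadline, "Within 10 calendar days after becoming aware of the event or as per local/regional regulations". A different row, "Procedure-Related Adverse Events and Adverse Device Effects", is limited by relatedness.
- Section 18.7 asks for every subject death to be reported within three calendar days. Relatedness is an item in the narrative, not a condition for reporting.

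On the analysis side, the synopsis and Table 6.1-1 list SAEs beside related adverse events and not within them. Section 11.1.2.1 defines Secondary Endpoint 1 as an SAE, with no further limit. Section 11.1.2.1.1 plans counts, the proportion of subjects with an SAE, a breakdown by relatedness, and Kaplan-Meier estimates at 90, 180 and 365 days after device activation.

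**The concern.** The footnote is part of the visit schedule that site staff work from. Under the protocol's own definitions, an unrelated SAE is an adverse event related to neither device nor procedure, so the exclusion covers it unless the reader supplies an exception that is not written.

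At stake is the content of a listed secondary safety endpoint. If a site leaves out unrelated SAEs, a subject whose only SAE was unrelated is analysed as event-free. The all-SAE proportion and the Kaplan-Meier estimates then come out too low. If only some sites do this, the pooled figure mixes two definitions. Section 20.2 has the Independent Medical Reviewer look at reportable events, so an event that was never entered would not reach that review either.

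**Working it through.** **Textual check.** The question is how each passage treats an SAE judged unrelated to both device and procedure.

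| Place | Treatment of an unrelated SAE |
|---|---|
| Footnote 3, sentence 1 | Reportable: SAEs are named, and the relatedness qualifier stands before AEs |
| Footnote 3, sentence 2, with Table 18.2-1 | Not collected, if read literally |
| Section 18.1, reporting list | Reportable |
| Section 18.1 on death, and section 18.7 | A fatal event is to be reported, with the death carried as the outcome of an SAE |
| Table 18.4-1, SAE row | Reportable; the row has no relatedness limit |
| Secondary Endpoint 1 | Counted |

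The death rules show the conflict most clearly. A death from an unrelated cause must be notified under section 18.7 and recorded under section 18.1 as the outcome of an SAE. Sentence 2 would leave no SAE to carry it.

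Three items support the broad reading less than they seem to:

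- The unrelated class in Table 18.3-1 is needed under either reading, because a site must judge relatedness before it can decide not to collect an event.
- The breakdown by relatedness in section 11.1.2.1.1 fits both readings, because an event can be related to the procedure and not to the device.
- The separate SAE row in Table 18.4-1 could hold procedure-related SAEs, so it points to full collection without proving it.

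Section 18.1, the death rules and Secondary Endpoint 1 establish the conflict without these.

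**Size.** The documents give no SAE rate and no basis for guessing how many sites would apply sentence 2 literally, so there is no plan figure to reproduce and no total to compute. Only a per-subject illustration is possible.

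- Inputs, from section 11.1.1.2: 120 procedure subjects and 20% attrition.
- Crude proportion: one subject whose only SAE is omitted changes it by 1/120 = 0.0083, or 0.83 percentage points.
- Kaplan-Meier at 12 months with no earlier censoring: also 1/120 = 0.83 points.
- Kaplan-Meier if it is the only event and all the attrition comes first: 0.20 × 120 = 24 censored, 120 − 24 = 96 at risk, and 1/96 = 0.0104, or 1.04 points.

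These figures are not bounds. The 12-month visit may take place up to three months before day 365, and completing it ends participation, so the number at risk late in the year need be neither 120 nor 96. A subject who also has a related SAE still counts in the crude proportion; only the Kaplan-Meier event date could change.

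**The case against.** The strongest reply is that nobody would be misled. Sentence 1 names SAEs separately from the restricted class of AEs, so sentence 2 is most naturally read as the complement of that class, meaning non-serious unrelated events. Section 18.1 and Table 18.4-1 say the same. Section 18.1 also has a default in favour of reporting: an event whose category is unclear is to be submitted. Deaths are reported separately under section 18.7, and section 20.1 has monitors reviewing source documents.

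Most of this stands. It makes omission unlikely and keeps the point minor. It does not remove the conflicting sentence: the definitions do not allow adverse events to be read as non-serious ones, and the protocol states no rule of precedence between the schedule and section 18.

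A reader might go further and infer that the trial will collect only related SAEs, so that Secondary Endpoint 1 is in effect a related-SAE endpoint. The documents do not support that. The Revision B entry in the change log speaks of limiting adverse event collection to related events, but it is a summary of changes, does not mention SAEs and does not override the current section 18. Nor does the procedure-related qualifier govern the whole list in sentence 1. It would then also restrict device effects and device deficiencies to procedure-related ones, and section 18.1 attaches it to adverse events only.

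It would equally be too strong to call sentence 2 the protocol's only exclusion. Section 18.1 also leaves out underlying and chronic conditions that have not worsened.

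**Conclusion.** The inconsistency is real and lies in the current text, but it is minor. It concerns which data are collected, not the choice of analysis. Full SAE collection is the better-supported reading; the sponsor must still confirm the intent, because the wording alone does not settle it.

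The effect on the all-SAE summaries is unknown and is zero if no site applies sentence 2 literally. The 0.83-point figure assumes 120 analysed subjects and one subject whose only SAE was unrelated and omitted. Any bias is downward and confined to summaries that section 11.1.2 treats as descriptive.

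A reader might infer that the trial's main conclusion or its device-safety findings are in doubt. They are not: the pad-weight primary endpoint, the sample size, the revision rates and the related-SAE rates do not depend on collecting unrelated SAEs.

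**What to change.** Reconcile footnote 3 with section 18 and Secondary Endpoint 1, by one of two routes:

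- If all SAEs are to be collected, as section 18 and the endpoint indicate, begin sentence 2 of footnote 3 with the words *Non-serious adverse events*.
- If only related SAEs are meant to be captured, limit section 18.1, the SAE row of Table 18.4-1 and Secondary Endpoint 1 to related SAEs. Label the endpoint that way wherever it appears, and make the death rules fit.

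Under either route, tell sites which rule applies. Under the first, also look for omitted unrelated SAEs during routine source-document monitoring. The footnote asks for these events to be noted in the medical records, so omissions should be recoverable.

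The cost is a short wording amendment, the IRB/EC/REB review that section 15.3 requires for any amendment, a notification to up to 30 sites, and some added attention during monitoring. No analysis method or sample size changes.
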